b. Controlled Oral Word Association Test (COWAT).⁴⁰ This is an assessment of word retrieval during which the patient is required to produce as many words in one minute that begin with either a specific letter (e.g., *F*, *A*, or *S*) or members of a specific category (e.g., *animals*, *fruit and vegetables*). Psychometrics: Cronbach's alpha = .83 for the number of items generated per condition; test-retest reliability r = .74; test-retest also has shown significant gains observed from first (*M*=39.7, *SD*=10.48) to second (*M*=42.5, *SD*=9.9) administration, t(1, 119)=4.19, p<.001.⁴¹

c. Boston Naming Test (BNT).⁴² The test consists of 60 pictures of items where each is presented one at a time for the patient to provide the name of the item depicted. The task will be split into two equivalent 30 item tests (Cronbach alpha = .88; whole sample agreement between forms kappa = .93; Graves et al., 2004). The test assesses visuoperceptual processing, access to semantic knowledge and access to and production of the name of the object, which marked word retrieval from a visual input. Internal consistency ranges from r = .78 to .96 across studies. Test–retest stability in cognitively normal adults varies as a function of time interval and sample composition and ranges from r = .59 to .92.⁴³

d. California Verbal Learning Test (CVLT-II).⁴⁴ The test is a list-learning task where the tester reads aloud a list, called "Monday's shopping list." The list contains sixteen common words, each of which belongs to one of four categories. The tester records how many items the patient remembers over several repeated trials and if the patient is making use of category information. There is also a delayed recall trial after 20 minutes. The test is an indirect measure of word retrieval in that successful word retrieval from semantic memory is needed to perform well in this episodic memory task. The CVLT-II has generally large test-retest correlation coefficients for the primary CVLT-II measures in both the standard/standard (range r = 0.80-0.84) and standard/alternate (range r = 0.61-0.73) cohorts, with reliability coefficients for primary measures ranging from 0.80 (e.g., total trials 1–5) to 0.84 (recognition discriminability).⁴⁵

Parallel versions are available for all of the above neuropsychological tests. Additional neuropsychological measures included will be (organized by domain of cognitive function):

a) General Cognitive: American National Reading Test (AMNART) for estimated IQ.⁴⁶ This test is chosen to determine if changes from treatment could be associated with IQ and to compare groups that may have differential responses to treatment.

b) Attention and Cognitive Flexibility: Trail Making Test parts A and B⁴⁷; Color Word Interference Test.³⁶

1. For Trails A and B, Trails A measures processing speed and simple attention, and Trails B utilizes the same cognitive components as Trails A with the additional executive function of alternating sequencing. This test is not a direct measure of retrieval but is used to assess for generalization or indirect improvement with HD tDCS. Test-retest reliability is reported as r = 0.745 for Trails A, r = .849 for Trails B, and r = .971 for B-A.⁴⁸

2. Delis-Kaplan Color Word Interference Test³⁶ measures processing speed in the control conditions of color naming and word reading with color word names written in a different ink color than the name measures inhibitory control, an executive function. This test is not a direct measure of retrieval but is used to assess for generalization with HD tDCS, particularly to compare to performance on the inhibitory aspects of the Semantic Selection Tasks. Internal consistency is reported as Cohen's alpha = .62-.86 over age groups from 9 to 89 years of age (Manual), and within in the age GWV, Cohen's alpha = .72-.86. Test-retest reliability is reported as Color Naming r = .76, Word Reading, r = .62, Inhibition r = .75, and Inhibition/Selection r = .65, with lower test-retest reliability coefficients for 50-89 year olds, r = .50-.57.³⁶

3. Digit Span Forwards and Backwards⁴⁹ measures simple attention with digit span forwards and working memory with digit span backwards. This is chosen not because it is to be directly affected by the HD tDCS, but to determine that verbal episodic memory increases are from improvements in attention (digits forward) and to determine if there is generalization to working memory (digits backward). Test-retest reliability coefficients for Digits forwards ranges from .66-.89 and Digits Backwards approximating 0.70.⁵⁰

c) Visual Memory: Rey-Osterrieth Complex Figure Test (Copy and Memory components)⁵¹ The task requires a subject to copy a complex geometric figure and then later to draw what aspects of the figure that they

still remember. It is included in this study as a check to determine if retrieval improvement is not only in verbal retrieval but also generalizes to nonverbal material retrieval. Reliability across alternate forms is reported as Copy r = .50, Immediate Recall r = .76, and Delayed Recall r = .69, and reliability over one year is Copy r = .18, Immediate Recall r = .47, and Delayed Recall r = .592.⁵²

d) Psychomotor Speed: Grooved Pegboard Test. This test of psychomotor speed utilizes placement of pegs into slots of varying orientations. It is included to assess the specificity of tDCS to retrieval versus generalization to processing speed and the possibility that improved processing speed might mediate improved retrieval. The test has good test-retest reliability (0.91 and 0.85 for right and left hands, respectively).^{53, 54}

e) Beck Depression Inventory.⁵⁵ (Beck et al., 1996) is a subjective questionnaire of depressive symptomatology. The test is not being used as a marker of retrieval, but to determine if mood improvement that may be secondary to HD tDCS application may be accounting for minor improvements in retrieval.⁵⁴ Cronbach's average alpha coefficient average around 0.9, ranging from 0.83to 0.96, test-retest reliability ranges between 0.73 to 0.96.^{56, 57}

2. EEG Tasks

a. Semantic Object Retrieval Test (EEG version).³³ The stimuli in this EEG paradigm comprise 112 pairs of words. There are 56 retrieval and 56 nonretrieval word pairs. The "retrieval" and "non-retrieval" attributes of the word pairs have been validated in previous studies with different groups of subjects. Words will be presented simultaneously one pair at a time for three seconds, with one word above the other. Between trials, a + sign will be presented for three seconds as a visual fixation target. Participants will be instructed to respond "yes" or "no" depending on whether they could think of any particular object upon seeing each word pair. Word stimuli will be presented on an LCD screen placed about 46 inches from the eyes using Stim2 software (Compumedics Neuroscan, USA). Responses will be made by pressing a button under the right index finger for *no*. The entire task lasts about 11 minutes. The retrieval trials index successful access to an object memory represent-ation including verbal information, with the correct nonretrievals indicating a memory search that leads to a conclusion that the features do not combine to activate an object memory.

b. Semantic Selection Tasks.^{34, 35, 58} This paradigm comprises three variants of the Go/NoGo task (200 trials each task) that require varying levels of semantic categorization: a) Single Car task (SC): The stimuli are a line drawing of a car (Go) and a line drawing of a dog (NoGo). Participants are required to not push a button for the dog (20% of trials) and to push for the car (80% of trials). b) Multiple Cars task (MC): This task includes 40 different exemplars of cars (Go) and 10 different exemplars of dogs (NoGo). The instructions for this task are identical to those in the SC task. Each drawing of the 40 cars and of the 10 dogs is presented 4 times over the course of the task. Successful response and inhibition is dependent on the ability to retrieve the concept based on abstraction and integration of salient perceptual features associated with each object, followed by object level identification. c) Object Animal task (OA): This task includes 160 different exemplars of objects (Go) (40 food items, 40 cars, 20 clothing items, 20 kitchen items, 20 body parts, and 20 tools) and 40 different exemplars of animals of varying visual typicality (NoGo). Participants are to push a button for items that are not animals. The OA task has the greatest semantic complexity, as correct categorization between multiple categories necessitates retrieval of object knowledge that relies on more than just perceptual features and a determination of category membership.³⁴ Overall, each task comprises 200 trials presented in random order, 160 (80%) of which are Go trials that require a button press and 40 (20%) of which are NoGo trials that require inhibition/withholding of a response. Each stimulus is presented for 300 ms followed by a 1700-ms blank fixation period. The Go trials indicate selection and retrieval of the correct object in semantic memory and the NoGo trials index inhibition of a response when retrieval of a memory does not lead to the search target.

3. EEG Procedure

Continuous EEG will be recorded from a 64-electrode elastic cap (Neuroscan Quickcap) while the participants are preforming the task, through a Neuroscan SynAmps2 amplifier and using Scan 4.5 software (Compumedics Neuroscan, USA; sampling rate: 1kHz, DC-200Hz). Electrode impedances will typically be below 10 k Ω . The reference electrode located at midline between Cz and CPz, and vertical electroocculogram (VEOG) will be

recorded at sites above and below left eye. Data will be processed off-line using scripts developed in our lab that implement functions from EEGLAB version 13⁵⁹ (http://www.sccn.ucsd.edu/eeglab) running under Matlab 7.11.0 (The MathWorks, Inc.). Preprocessing will consist of down-sampling to 512 Hz, removing data recorded from poorly functioning electrodes, and correcting for stereotyped artifacts including eye blinks, lateral eye movements, muscle, line noise, and heart rate using the "Runica" algorithm (with the *extended*, *1* option)⁵⁹, an implementation of the logistic infomax independent component analysis algorithm.⁶⁰ Stereotyped artifacts will be identified by visual inspection of the spatial and temporal representation of the independent components. Continuous data will be segmented into 2-second non-overlapping epochs spanning from 500 ms before to 1800 ms after the presentation of the visual stimuli. Epochs containing high amplitude, high frequency muscle noise, and other irregular artifacts will be removed. Only trials to which the subject responded correctly and those without artifacts will be subjected to further analysis, retaining on average 75 percent of all epochs. We will estimate data for missing electrodes by interpolation. The interpolated data will be re-referenced to the average reference.⁶¹

D. HD tDCS Treatment Procedures

High-definition (HD)-tDCS uses arrays of smaller electrodes, combinations of which can be optimized for targeting. So far, HD-tDCS has been shown to reliably target specific brain areas and proved to produce plastic changes that may outlast conventional tDCS. ⁶². A study comparing conventional tDCS with a HD-tDCS design using a set of small electrodes approximating the conventional set-up (covering the large pad-electrodes) found that the HD-tDCS approach achieved electrical fields with greater focality (80% improvement) and higher target intensity (98% improvement) at cortical targets using the same total current applied.⁶³

Cap. The EEG cap is gently secured on the head of a subject and positioned with Cz at the vertex, as measured using surface anatomical landmarks, and defined as the intersection of the nasion–inion and interaural lines.

Electrodes. tDCS is delivered with Sintered Ag/AgCl disc electrodes using customized high-definition electrode with 8-mm diameter resulting in a ~85 \pm 5 mm². The electrode were then filled with > 3 mL of conductive Gel into which the Ag/AgCl disc electrode was immersed. The cotton swab was used to adjust the gel and hair until the electrode resistance was less than 10 k Ω prior to stimulation. The anode was placed over Fz according to the International 10-20 EEG system, corresponding to the approximate location of the pre-SMA. Four return cathodal electrodes were placed approximately 5 cm radially from Fz, corresponding to locations FPz, F7, F8 and Cz (see Figure 8). The preparation procedure consisted of exposing the scalp by separating the hair underlying each electrode and adding approximately 1.5 mL of highly conductive gel. Contact quality and impedance levels were verified for each electrode before each stimulation session began.

Stimulation. Electrical stimulation is performed using a constant voltage Cortical Stimulator (Model D185, Digitimer Ltd, UK, maximal output 1000 V/1.5 A) with single square-wave 50-µs pulses (0.1 A/µs rise time). The adaptor measured resistance prior to stimulation, and divide current during stimulation. HD tDCS will be delivered in the active condition for 20 minutes of 1 milliamp high definition tDCS per session and administered for 10 total sessions on separate days (10 sessions over 10-14 days). This provides focal delivery of current maximally at the preSMA. There is no sensation associated with stimulation at this level, so that the sham condition will consist of placing the HD tDCS cap in place for the 10 sessions of 20 minutes each, but without delivering electrical stimulation. After each session, patients will be administered a standard post-treatment symptom questionnaire (e.g., assessing for skin irritation, fatigue).⁶⁴

E. Potential Problems

1. There is the possibility that the HD tDCS will affect regions other than the preSMA. This will be assessed by reviewing changes in neuropsychological test measures.

2. There is also the possibility that stimulation will be ineffective because the target tissues have been too badly damaged. We will monitor for response patterns consistent with ineffective stimulation.

3. There could be difficulty in recruiting subjects, but we have not only identified the individuals referred to [name] cohort as noted in the subjects section, but also have the availability to recruit subjects

through the Dallas VAMC, and we have been quite successful in recruiting for two ongoing veteran studies at our Center through local advertising.

4. Some individuals with Gulf-War–related complaints and impaired performance will have these difficulties from etiologies other than GWI. It is possible that individuals with complaints of symptoms not attributable to GWI will have abnormal findings based on some other underlying pathology (e.g., traumatic brain injury, depression, thyroid disease, etc.). We have performed studies in aging⁶⁵, concussion ⁶⁶, dementia⁶⁷, ⁶⁸, and depression⁶⁹ using several of the tests proposed for this study and the pattern of performance in these groups differs from those with GWI. We will try to exclude individuals with co-morbidities that result in retrieval deficits similar to GWI and will be mindful to assess for age and possible dementing-related factors affecting outcome.

STATISTICAL PLAN

The efficacy of HD tDCS will be assessed on each outcome. For the cognitive-behavioral measures (i.e., from SORT, COWA, BNT, CVLT, Trails A & B, Color Word Interference, Digits Forward & Backward, Rey-Osterrieth Complex Figures Test, Grooved Pegboard Test, and Beck Depression Inventory), a mixed-model MANOVA initially will be used to test for omnibus group (active vs sham) effects over time (i.e., Group X Time interaction effects). Given a significant multivariate effect, separate univariate mixed-model ANOVAs for each cognitive-behavioral measure will be evaluated for group (active vs sham) effects over time, and significant interaction effects will be followed up by separate pre- versus post-intervention evaluations for each tDCS group. Verbal fluency has been associated with sex, age, and education^{70, 71 but see 72}; thus, these variables will be included in the models. Additionally, potential mediating effects of IQ (based on NAART) and pre-test to post-test change in executive function, simple attention, working memory, processing speed, and depression (measured via Trails A & B, Color Word Interference, Digits Forward & Backward, Rey-Osterrieth Complex Figures Test, Grooved Pegboard Test, and Beck Depression Inventory) will be explored through covariate mediation modeling. For all testing, data will be thresholded for False Discovery Rates (FDR).

After removing artifacts and segmenting EEG data into multiple trial-by-trial EEG epochs (-200 ms to 1800 ms for SORT and to 1500 ms for SIT), we will apply the STAT-PCA technique that we published, and with which we have longitudinal experience ^{32, 73} for ERP and time frequency data. Baseline corrected ERPs at each space-time (ST) point, and log normalized squared absolute values at each space, time, frequency (STF) point will be calculated and used as input for the inferential stage of STAT-PCA. The statistical model will include the additive effects of group (active vs sham) and time and higher-order additive effects of group, time, and condition (SORT: Bind vs Nonbind; Semantic Selection: Trial-Type [Go vs No-Go] X Categorization [Simple vs. Moderate vs. Complex) on ERP at each space-time point and log power at each STF. Both withinand between-subject variance components will be included. Interaction contrast *t*-statistics for each ERP ST and spectral STF point will be calculated to assess the influence of the interaction terms on log power, and planned t-contrasts will be calculated from condition differences between the groups. Mean differences that survive a threshold of 5% FDR will be stored as a ST and STF arrays and entered into the sequential PCA. For ERP data, the ST array will be put in a matrix in which columns index space and rows index time. For ERP data, PCA will be performed and will return a set of eigenvalues and eigenvectors, which will be subjected to Parallel Analysis ⁷⁴ to determine the number of factors to retain. Only eigenvalues above the 95% confidence intervals of the null distribution will be retained. The retained eigenvectors will be varimax rotated and used to calculate the factor scores by projecting the original dataset onto the eigenvectors. The resulting factor scores will be reshaped such that the columns index electrodes and the rows index time points, and PCA will be performed on this matrix. Factor retention will be determined as in the first sequence. The resulting eigenvectors will represent topographies and their corresponding factor scores will represent the time courses for the interaction effects.

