Objective #4: Each subject will undergo a detailed neuropsychological battery to characterize his or her cognitive and behavioral status—including targeted tests that should be affected by improved verbal retrieval, tests of cognitive functions to which the treatment may generalize, and tests consisting of purportedly unrelated functions to account for global, generalized cognitive improvement. They will also undergo pre-treatment EEG (SORT task with EEG, Semantic Selection task with EEG). These will be used as outcome measures for the treatment trial. The two primary outcome measures will be the COWAT and CVLT. Secondary outcome measures will be SORT and Semantic Selection task, performance and ERP for both sets of tasks.

Objective #5: These subjects will then be enrolled in the active treatment aspect of the study. Enrollment of 80 participants is the target for enrollment in the active phase of the treatment trial. Half the subjects will first receive HD tDCS at 1 mA for 20 minutes over the preSMA region for 10 daily sessions (1 session 5 days per week for a 2 week period). The remaining subjects will initially receive sham HD tDCS; after all follow-up evaluations are completed, they will receive the active HD tDCS treatment.

Objective #6: Each subject will receive follow-up neuropsychological and EEG testing at 1 week, 3 months, and 6 months after treatment. This last time point for evaluation extends from our preliminary work showing that later, further improvement in electromodulation treatments can occur at 6 months post-treatment. HD tDCS active treatment subjects enrolled early in the study will be followed longer than 6 months if agreeable to assess length of effect.

Following completion of this clinical trial, we will be able to determine whether HD tDCS is an effective treatment for the verbal retrieval deficits associated with GWI. An HD tDCS cap is a relatively inexpensive piece of equipment that can be re-used many times for multiple patient treatments. These caps are readily available, and the application of the treatment regimen is straightforward to administer. Thus, this treatment can be utilized in any VA medical center or clinic around the nation. In addition, the neuro-psychological tests and ERP/time frequency findings may function as clinical markers for diagnosis and treatment efficacy in subsequent treatment trials to measure treatment response.

SPECIFIC AIMS

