Hypothesis #2c: An increase in false negative errors and a decreased "Go"P3 ERP response on the Semantic Selection Tasks is indicative of an impaired ability to select a correct memory for retrieval.³³ Conversely, there will be increased false positive errors and a decreased "NoGo" P3 ERP on the Semantic Selection Tasks if a patient cannot inhibit an incorrect memory. *We hypothesize that following HD tDCS therapy, there will be a normalization of the patient's behavior (reduced errors, improved RTs) and/or ERP responses (increased P3 amplitudes for Go and/or NoGo trials) due to modulation of the retrieval circuit, with the changes based on the pre-treatment impaired retrieval function (selection and/or inhibition).*

CLINICAL TRIAL

A. General Experimental Approach.

1. We will screen 120 GWI patients who report subjective word-retrieval deficits over the phone with the COWAT.

2. A subject who on the phone screen has a subjective complaint and decrement in COWAT performance will then be consented and enrolled in person at CBH, and then screened to determine that they have GWI and objective evidence of a verbal retrieval impairment on neuropsychological testing.

3. If a subject scores > 2 SD below the mean on any of the following – the SORT clinical test, COWAT, BNT, and/or CAVLT, the subject will be enrolled in the treatment phase of the study and classified using the CDC criteria for subtype of Gulf War Illness.

4. Subjects will undergo a pre-treatment battery of detailed neuropsychological tests and EEG (SORT and Semantic Selection tasks with ERP). These will be used as outcome measures for the treatment trial.

5. We will enroll 80 subjects in treatment with one-half of the subjects receiving HD tDCS at 1 mA for 20 minutes over the preSMA region for 10 daily sessions; the other half of the subjects will initially receive sham HD tDCS and, after all follow-up evaluations are completed, they will receive active HD tDCS treatment. Participants will be randomly assigned to stimulation and sham conditions via algorithm.

6. Determine at 1 week, 3 months, and 6 months post-last-treatment whether the therapy has been effective by repeating the outcome measures (parallel versions when available) of the SORT, COWAT, BNT, CVLT, and ERP tasks.

B. Subject Recruitment

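### No order of test forms is set for the repeated CVLT and BNT, and the within-arm pre/post tests and active-only late follow-up would count practice and form shifts as change

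*Combined protocol and SAP*

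**What the plan says.** Item 6 of the General Experimental Approach assesses the therapy after treatment by "repeating the outcome measures (parallel versions when available) of the SORT, COWAT, BNT, CVLT, and ERP tasks". The Neuropsychological Measures section adds: "Parallel versions are available for all of the above neuropsychological tests". It does not say how many versions each test has.

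- **BNT:** "The task will be split into two equivalent 30 item tests", with "whole sample agreement between forms kappa = .93".
- **CVLT-II:** retest correlations are given for "standard/standard (range r = 0.80-0.84) and standard/alternate (range r = 0.61-0.73) cohorts". No other form is mentioned.
- **COWAT:** "test-retest reliability r = .74", and "significant gains observed from first (*M*=39.7, *SD*=10.48) to second (*M*=42.5, *SD*=9.9) administration".

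CVLT and BNT are given at in-person screening (Subject Recruitment, Stage 2), possibly again before treatment (Stage 3), and at three follow-ups. COWAT is also given by phone. COWAT and CVLT are the two primary outcomes.

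The Statistical Plan tests Group x Time, active against sham, first by MANOVA and then by univariate mixed-model ANOVA. A significant interaction is followed by pre/post evaluations within each arm. Objective #6 says that "later, further improvement in electromodulation treatments can occur at 6 months post-treatment", and follows early-enrolled active subjects beyond 6 months to see how long the effect lasts. Neither the protocol nor the Statistical Plan gives a form sequence, a re-use rule or a form term.

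**The concern.** With two forms and four or five testings, at least two or three testings must re-use a form. If everyone follows one fixed order, form is tied to visit. A change from baseline then mixes treatment with practice, with having seen the material before, and with any difference in difficulty between forms. A concurrent sham arm removes these shifts only where the analysis subtracts it. The within-arm follow-up tests do not, and beyond 6 months there is no sham arm left to subtract.

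For CVLT there is a second effect. By the protocol's own figures, a visit on the baseline form correlates more strongly with baseline than a visit on the other form. The same true effect is then estimated more precisely at some visits than at others. Objective #6 expects later improvement, so a pattern of no significance at 1 week and significance at 3 months could be taken as the anticipated result.

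**Working it through.** **1. The protocol's retest figure.** The COWAT gain is 42.5 − 39.7 = 2.8 words, and 2.8/10.48 = 0.27 baseline SD. With r = .74, the SD of the difference is √(10.48² + 9.9² − 2 × .74 × 10.48 × 9.9) = 7.37. With n = 120 (from the stated 119 df), t = 2.8/(7.37/√120) = 4.16. The protocol states 4.19, so the figure reproduces to rounding.

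**2. Within-arm pre/post tests, no treatment effect.** SD of change, in baseline SDs, is √(2(1 − r)). The test is a paired t with n = 40, two-sided 0.05 (assumed, since the plan names only FDR).

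| Test | r | SD of change | Chance that a 0.27 SD gain is significant |
|---|---|---|---|
| COWAT | .74 | 0.72 | 64% |
| CVLT, alternate form | .61 to .73 | 0.88 to 0.73 | 47% to 62% |
| CVLT, same form | .80 to .84 | 0.63 to 0.57 | 75% to 84% |

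The CVLT rows borrow the COWAT gain, which is an assumption. With a shift of only 0.1 SD, the CVLT range is 11% to 19%.

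**3. Between-arm comparison under a shared order.** Simulation: 5,000 trials, 40 per arm, forms A, B, A, B at baseline, 1 week, 3 months and 6 months; r = .82 for the same form and .67 for different forms (mid-ranges). The assumed shifts were ±0.2 SD for form B and 0.27 SD for re-use. Bias in active minus sham was 0.00 and type I error 0.050 to 0.056 at every visit. Within an arm, with form B harder by 0.2 SD and no treatment effect, mean change was −0.20, +0.27 and +0.07 SD at the three visits: an apparent late gain that wanes.

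**4. Precision by visit, CVLT.** The ratio of change variances is (1 − .67)/(1 − .82) = 1.8. The standard error of active minus sham is √(2(1 − r)) × √(2/40), which is 0.126 to 0.141 SD on the baseline form and 0.164 to 0.197 SD on the other. Power of a two-sample t on change, 40 per arm, two-sided 0.05:

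| True difference (assumed) | Same form, r = .82 | Other form, r = .67 | Half of each arm on each |
|---|---|---|---|
| 0.4 SD | 84% | 59% | 70% |
| 0.5 SD | 96% | 78% | 87% |
| 0.61 SD | 99% | 91% | 97% |

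The last column uses the average of the two variances. In the simulation with a constant 0.5 SD effect, non-significance at 1 week with significance at 3 months occurred in about 20% of trials under A, B, A, B, against 3.6% with one form throughout (0.4 SD: 31% against 11%).

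**5. Checking form sequences.** ABAB and BABA both give other, same, other relative to baseline, so power by visit stays 78%, 96%, 78% at 0.5 SD. Form-seen-before is then no, no, yes, yes for everyone and cannot be separated from visit: the design matrix (intercept, three visit indicators, form, seen before) has rank 5 of 6. Adding AABA and BBAB (same, other, same) puts half of each arm on the baseline form at every visit and gives rank 6.

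**The case against.** The strongest reply is that the trial is randomised against concurrent sham and its efficacy test is Group x Time. This stands. A reader might infer that changing forms biases the main result, or that form differences are bound to be read as onset or duration. The documents do not support that: under a shared order these shifts cancel between arms.

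Four further points carry weight.

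- The within-arm tests run only after a significant interaction, so the percentages in step 2 are not the trial's false-positive rate. They show how readily practice alone would make an arm, such as sham, look improved, and the same shift would add to the active arm's gain.
- The plan contains no change-score t-test at each visit. The power figures illustrate precision by visit, not the planned test. Adjusting for baseline narrows the gap without closing it: at 0.5 SD, 0.961 to 0.985 on the same form and 0.806 to 0.905 on the other (normal approximation).
- The gap depends on the effect size. At 0.61, the smallest effect size used in the sample-size section (there for verbal fluency), it is 99% against 91%; at 1.12 both are about 100%.
- Two CVLT forms is an inference, since no count is given. Form-dependent reliability is reported for CVLT only. BNT is not a primary outcome, and its halves agree closely.

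**Conclusion.** The point holds as a modest, inexpensive improvement. The between-arm test is sound if both arms share one form order, although the plan does not say that they do. What needs changing is how timing and duration would be read: from within-arm pre/post tests and active-only data that do not subtract practice, re-exposure or form difficulty, and across CVLT visits that may differ in precision.

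The within-arm effect is about 64% for COWAT, and 47% to 84% for CVLT if its gain matches COWAT's. The precision effect is about 96% against 78% at 0.5 SD. These sizes assume two-sided 0.05, two CVLT forms, 40 completers per arm, and that the quoted reliabilities apply at the trial's retest intervals. Those reliabilities are also ranges across several CVLT scores, so pairing their extremes may overstate the contrast for any one score.

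**What to change.** 1. In the Statistical Plan, replace the within-arm pre/post follow-up with active-minus-sham contrasts at each visit, adjusted for baseline. Base claims about onset and duration on these alone, comparing the estimates and their intervals between visits rather than which visits reach significance. Label active-only data beyond 6 months as descriptive.
2. Assign form sequences at random, balanced within arm, from a set in which half of each arm repeats its baseline form at each visit. ABAB, BABA, AABA and BBAB, counted from the pre-treatment test, meet this; ABAB and BABA alone do not. If screening is a separate testing, fix its form too and count it as exposure. Include a form term. Add a prior-exposure term only if the chosen sequences make it estimable separately from visit.

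The cost is one more column in the randomisation list, one or two model terms, and some precision at any visit where all patients would otherwise have repeated the baseline form. At 0.5 SD, that visit goes from 96% to 87%, while the others rise from 78% to 87%. The sequences must be set before testing starts: if form stays tied to visit, the two cannot be separated afterwards.
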